#### 5.1.2 Subject Inclusion Criteria

In order to be eligible for participation in this trial, the subject must:

1. Be willing and able to provide written informed consent for the trial. Study entry is defined as the date that subject provides written informed consent. The subject may also provide consent for Future Biomedical Research. However, the subject may participate in the main trial without participating in Future Biomedical research.
2. Be  $\geq 18$  years of age on the day of providing written informed consent.
3. Have an ECOG performance status score of  $\leq 1$ .
4. Have an interval of  $\geq 3$  weeks since chemotherapy ( $\geq 6$  weeks for nitrosoureas or mitomycin C), immunotherapy, hormone therapy or any other anticancer therapy (including investigational) or surgical intervention resection, or  $\geq 3$  half-lives for monoclonal antibodies, or  $\geq 5$  half-lives for other non-cytotoxic agents (whichever is longer).
5. Female subjects of childbearing potential must have a negative urine or serum pregnancy test within 72 hours prior to receiving the first dose of study medication. If the urine test is positive or cannot be confirmed as negative, a serum pregnancy test will be required.
6. Female subjects of childbearing potential should be willing to use an adequate method of contraception as outlined in section 5.7.3 - Contraception, for the course of the study through 90 days after the last dose of study medication. Note: Abstinence is acceptable if this is the usual lifestyle and preferred contraception for the subject.
7. Male subjects of childbearing potential 5.7.3 – Contraception, starting with the first dose of trial treatment through 90 days after the last dose of study medication. Note: Abstinence is acceptable if this is the usual lifestyle and preferred contraception for the subject
8. Demonstrate adequate organ function as defined in [Table 1](#) below. All screening labs should be performed within 7 days of treatment initiation.

Table 1 Adequate Organ Function Laboratory Values

System	Laboratory Value
Hematological	
Absolute neutrophil count (ANC)	AML Subjects = No Limit DLBCL Subjects = $\geq 1.0 \times 10^9/L$
Platelets	AML Subjects = No Limit DLBCL Subjects = $\geq 150 \times 10^9/L$ (4 weeks without transfusion)
Hemoglobin	AML Subjects = No Limit DLBCL Subjects = $\geq 8.0 \text{ g/dL}$ (4 weeks without transfusion)
Renal	

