### 5.7.3 Contraception

MK-8628 may have adverse effects on a fetus in utero. Furthermore, it is not known if MK-8628 has transient adverse effects on the composition of sperm.

For this trial, male subjects will be considered to be of non-reproductive potential if they have azoospermia (whether due to having had a vasectomy or due to an underlying medical condition).

Female subjects will be considered of non-reproductive potential if they are either:

- 1) postmenopausal (defined as at least 12 months with no menses without an alternative medical cause; in women  $< 45$  years of age a high follicle-stimulating hormone (FSH) level in the postmenopausal range may be used to confirm a post-menopausal state in women not using hormonal contraception or hormonal replacement therapy. In the absence of 12 months of amenorrhea, a single FSH measurement is insufficient.);

OR

- 2) have had a hysterectomy and/or bilateral oophorectomy, bilateral salpingectomy, or bilateral tubal ligation/occlusion at least 6 weeks prior to screening;

OR

3) has a congenital or acquired condition that prevents childbearing.

Female and male subjects of reproductive potential must agree to avoid becoming pregnant or impregnating a partner, respectively, while receiving study drug MK-8628 and for 90 days after the last dose of study drug. Subjects must comply with one of the following:

1) practice abstinence† from heterosexual activity;

OR

2) use (or have their partner use) acceptable contraception during heterosexual activity.

Acceptable methods of contraception are‡:

Single method (one of the following is acceptable):

- intrauterine device (IUD)
- vasectomy of a female subject's sole male partner
- contraceptive rod implanted into the skin

Combination method (requires use of two of the following):

- diaphragm with spermicide (cannot be used in conjunction with cervical cap/spermicide)
- cervical cap with spermicide (nulliparous women only)
- contraceptive sponge (nulliparous women only)
- male condom or female condom (cannot be used together)
- hormonal contraceptive: oral contraceptive pill (estrogen/progestin pill or progestin-only pill), contraceptive skin patch, vaginal contraceptive ring, or subcutaneous contraceptive injection

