†Abstinence (relative to heterosexual activity) can be used as the sole method of contraception if it is consistently employed as the subject's preferred and usual lifestyle and if considered acceptable by local regulatory agencies and ERCs/IRBs. Periodic abstinence (e.g., calendar, ovulation, sympto-thermal, post-ovulation methods, etc.) and withdrawal are not acceptable methods of contraception.

‡If a contraceptive method listed above is restricted by local regulations/guidelines, then it does not qualify as an acceptable method of contraception for subjects participating at sites in this country/region.

Subjects should be informed that taking the study medication may involve unknown risks to the fetus (unborn baby) if pregnancy were to occur during the study. In order to participate in the study, subjects of childbearing potential must adhere to the contraception requirement

(described above) from the day of study medication initiation (or 14 days prior to the initiation of study medication treatment [Day 1] for oral contraception) throughout the study period up to 90 days after the last dose of trial therapy. If there is any question that a subject of childbearing potential will not reliably comply with the requirements for contraception, that subject should not be entered into the study.

Monthly pregnancy testing is recommended per local standards if applicable.

**For countries (e.g., Sweden and Norway) or sites that follow the Clinical Trial Facilitation Group (CTFG) guidance, please use the following:**

MK-8628 may have adverse effects on a fetus in utero. Furthermore, it is not known if it may have transient adverse effects on the composition of sperm. Therefore, non-pregnant, non-breastfeeding women may only be enrolled if they are willing to follow the CTFG Guidance (Final Version 2014-09-15, Sections 4.1 and 4.2) for highly effective birth control as outlined below, or are considered to be highly unlikely to conceive. Highly unlikely to conceive is defined as 1) surgically sterilized, or 2) postmenopausal (a woman who is  $\geq 45$  years of age and has not had menses for greater than 1 year will be considered postmenopausal), or 3) not heterosexually active for the duration of the study. Subjects should use birth control methods that can achieve a failure rate of less than 1% per year when used consistently and correctly and are considered as highly effective birth control methods. Such methods include:

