## **5.10 Beginning and End of the Trial**

The overall trial begins when the first subject signs the informed consent form. The overall trial ends when the last subject completes the last study-related phone-call or visit, discontinues from the trial or is lost to follow-up (i.e. the subject is unable to be contacted by the investigator).

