### **7.2.2 Reporting of Pregnancy and Lactation to the Sponsor**

Although pregnancy and lactation are not considered adverse events, it is the responsibility of investigators or their designees to report any pregnancy or lactation in a subject (spontaneously reported to them) that occurs during the trial.

Pregnancies and lactations that occur after the consent form is signed but before treatment allocation/randomization must be reported by the investigator if they cause the subject to be excluded from the trial, or are the result of a protocol-specified intervention, including but not limited to washout or discontinuation of usual therapy, diet, placebo treatment or a procedure. Pregnancies and lactations that occur from the time of treatment allocation/randomization through 30 days following cessation of Sponsor's product must be reported by the investigator. All reported pregnancies must be followed to the completion/termination of the pregnancy. Pregnancy outcomes of spontaneous abortion, missed abortion, benign hydatidiform mole, blighted ovum, fetal death, intrauterine death, miscarriage and stillbirth must be reported as serious events (Important Medical Events). If the pregnancy continues to term, the outcome (health of infant) must also be reported.

Such events must be reported within 24 hours to the Sponsor either by electronic media or paper. Electronic reporting procedures can be found in the EDC data entry guidelines. Paper reporting procedures can be found in the Investigator Trial File Binder (or equivalent).

Although pregnancy and lactation are not considered adverse events, it is the responsibility of investigators or their designees to report any pregnancy or lactation in a subject (spontaneously reported to them), including the pregnancy of a male subject's female partner that occurs during the trial.

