Pregnancies and lactations of subjects and female partners of male subjects from the time the consent form is signed but before treatment allocation/randomization must be reported by the investigator if they cause the subject to be excluded from the trial, or are the result of a protocol-specified intervention, including but not limited to washout or discontinuation of usual therapy, diet, placebo treatment or a procedure. Pregnancies and lactations of subjects and female partners of male subjects that occur from the time of treatment allocation/randomization through 30 days following cessation of Sponsor's product must be reported. All reported pregnancies must be followed to the completion/termination of the pregnancy. Pregnancy outcomes of spontaneous abortion, missed abortion, benign

hydatidiform mole, blighted ovum, fetal death, intrauterine death, miscarriage and stillbirth must be reported as serious events (Important Medical Events). If the pregnancy continues to term, the outcome (health of infant) must also be reported.

Such events must be reported within 24 hours to the Sponsor either by electronic media or paper. Electronic reporting procedures can be found in the EDC data entry guidelines. Paper reporting procedures can be found in the Investigator Trial File Binder (or equivalent).

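### Contraception is required to 90 days after the last dose, but the dated duty to report pregnancies stops at 30 days, leaving days 31–90 only partly covered

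*Combined protocol and SAP*

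**What the plan says.** **Contraception period.** Inclusion criteria 6 and 7 (Section 5.1.2) both run to 90 days after the last dose. For men the wording is "starting with the first dose of trial treatment through 90 days after the last dose of study medication". Section 5.7.3 repeats this for both sexes: "while receiving study drug MK-8628 and for 90 days after the last dose of study drug". Its reasons are possible fetal harm and, for men, that "it is not known if MK-8628 has transient adverse effects on the composition of sperm". The alternative text for sites following the CTFG guidance also states 90 days, but then points to Section 7.2.2 for the length of the follow-up period.

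**Reporting period.** Section 7.2.2 gives two dated duties. For subjects, pregnancies and lactations are covered "through 30 days following cessation of Sponsor's product must be reported by the investigator". The later paragraph extends this to "female partners of male subjects that occur from the time of treatment allocation/randomization through 30 days following cessation of Sponsor's product".

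**Undated provisions.** Section 7.2.2 opens with a general duty to "report any pregnancy or lactation in a subject (spontaneously reported to them) that occurs during the trial". Section 5.10 defines when that period closes: "The overall trial ends when the last subject completes the last study-related phone-call or visit". Section 5.7.4 covers female subjects who conceive while on treatment, and has a sentence on male subjects' partners with no day limit. On testing, Section 5.7.3 says only: "Monthly pregnancy testing is recommended per local standards if applicable".

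**The concern.** The protocol treats the 90 days after the last dose as a period in which conception should not happen. A site that follows the dated reporting rule stops one third of the way through it. After day 30, whether a pregnancy reaches the sponsor depends on the subject volunteering it and on the trial still being open.

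The gap is clearest for a female subject who stops for progression. She has no fixed visit in days 31–90, Section 5.7.4 covers her only while on treatment, and the serious-event route after day 30 requires a judgement that the event is drug-related. A pregnancy with no adverse outcome, or with one not attributed to the drug, could go unreported, although these are the cases needed to interpret exposure near conception.

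There is also an internal inconsistency. The CTFG paragraph of 5.7.3 refers to a follow-up period in 7.2.2 whose only dated post-treatment length is 30 days, so those sites can read two end dates for contraception itself.

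**Working it through.** The plan gives no figure to reproduce. The check compares stated windows.

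**Inputs**
- Contraception: 90 days after last dose (5.1.2, 5.7.3).
- Dated pregnancy reporting: 30 days after cessation (7.2.2, both paragraphs).
- Safety visit: day 30 ± 5 (7.1.5.4.1); the flow chart in Section 6.0 has ± 3.
- Disease follow-up without progression: every 6 weeks ± 3 days (AML) or every 12 weeks ± 7 days (DLBCL), ending at progression or new anticancer treatment (7.1.5.4.2).
- One subject still on treatment (1.0).

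**1. Size of the mismatch**
- 90 − 30 = 60 days (days 31–90).
- 60 / 90 = 67% of the post-dose contraception period.

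**2. Fixed contacts in days 31–90**

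| Subject | Calculation | Days | Fixed visits |
|---|---|---|---|
| AML, no progression | 42 ± 3; 84 ± 3 | 39–45; 81–87 | 2 |
| DLBCL, no progression | 84 ± 7 | 77–91 | 1 (may fall a day late) |
| Either, after progression or new therapy | – | – | 0 |

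These days assume that discontinuation coincides with the last dose. Section 7.1.5.3 allows a lag of up to 3 days, which moves the ranges but not the nominal visit counts. No pregnancy question or test is listed at these visits. Follow-up of unresolved related adverse events can add contacts on no fixed schedule. Because Section 1.0 now supersedes earlier procedures, the table describes the underlying schedule rather than what the remaining subject will necessarily undergo.

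**3. The remaining subject**

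Suppose this subject stops for progression with no unresolved related event. The last scheduled visit is then at 30 ± 5 = days 25–35, and under 5.10 the trial can end there.
- Trial ends by day 30: days 31–90 = 60 days lie outside both the dated and the during-the-trial duties.
- Trial ends on day 35: days 36–90 = 55 days.

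**4. What the other provisions cover in days 31–90**
- *General duty in 7.2.2:* spontaneous reports only, while the trial is open.
- *5.7.4, female subjects:* on treatment only.
- *5.7.4, partners:* undated, so it does reach this period.
- *7.2.3.1:* serious events at any time, but after day 30 only if considered related. Table 10 counts a congenital anomaly as serious whenever it is diagnosed. Section 7.2.2 classes adverse outcomes such as miscarriage and stillbirth as serious.
- *Flow chart footnote i:* drug-related adverse events after 30 days; 7.2.2 says that pregnancy is not an adverse event.
- *Monthly testing:* a recommendation dependent on local standards, with no end date.

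No entry is a duty to report any pregnancy in a female subject throughout days 31–90 regardless of attribution.

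**5. After the change**

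With 90 days in both 7.2.2 paragraphs the mismatch is 90 − 90 = 0 days.

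**The case against.** The strongest reply is that the remaining gap is small and its safety weight low.

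- **Existing cover is wide.** The trial runs until the last subject's last contact, so the during-the-trial duty reaches days 31–90 for any subject whose 90 days finish before then. The hard gap is essentially the final subject. This stands, subject to the reliance on spontaneous report.
- **Follow-up is already required.** Section 7.2.2 says every reported pregnancy is followed to its end, with no day limit. This stands: what lacks a date is the initial report.
- **Thirty days is a coherent choice.** It matches the AE, SAE and ECI windows, and the half-life in Section 4.2.2.1 is about 5–6 hours. Thirty days is 720 hours, or 720 / 6 = 120 half-lives at the slower value. This lowers the likely exposure of a late conception. It does not remove the inconsistency, since the sponsor chose 90 days of contraception with the same half-life in view.
- **CTFG sites already have the 90-day figure** just above the cross-reference. True, so that part is slight.
- **The change does not improve ascertainment much.** With no test or call added, capture after day 30 still depends on the subject telling the site. This stands in part. A reminder helps, and the site would have a clear duty once told, whether or not the trial had closed.
- **A text change needs ethics review and perhaps revised consent information,** for a discontinued program with one treated subject. This is fair, and belongs in the cost.

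**Conclusion.** The concern holds and is minor. The dated reporting duty omits 60 of the 90 days in which the protocol requires contraception, and the partial cover does not amount to an attribution-free duty for female subjects in that period. For the one remaining subject the number of additional reporting subjects (that subject or a partner) is bounded between 0 and 1. This is a bound and not an expected value, because reproductive potential is not stated. The 55–60-day figure rests on that subject stopping for progression with no unresolved related event. The DLT endpoint, RP2D decision, sample size and analyses are unaffected.

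**What to change.** 1. In both dated paragraphs of 7.2.2, separate pregnancy from lactation. Require every pregnancy in a subject or a male subject's partner, from allocation to 90 days after the last dose, to be reported whether or not the trial has closed. Keep lactation at 30 days. If the sponsor prefers 90 days for both, the text should say so. The existing requirement to follow reported pregnancies to outcome can stay as it is.
2. In the CTFG paragraph of 5.7.3, replace the reference to the 7.2.2 follow-up period with 90 days after the last dose.
3. At the existing 30-day visit, remind the subject to tell the site of any pregnancy up to day 90.
4. Leave the AE, SAE and ECI windows at 30 days.

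The cost is two reworded sentences, one phrase and a verbal reminder, plus the ethics review of a text amendment and any consent update that it triggers. It adds no visit or test, and a few extra reports at most. The paper route in 7.2.2 remains usable after the eCRF closes.

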### 7.2.3 Immediate Reporting of Adverse Events to the Sponsor

#### 7.2.3.1 Serious Adverse Events

A serious adverse event is any adverse event occurring at any dose or during any use of Sponsor's product that:

- Results in death;
- Is life threatening;
- Results in persistent or significant disability/incapacity;
- Results in or prolongs an existing inpatient hospitalization;
- Is a congenital anomaly/birth defect;
- Is an other important medical event.

**Note:** In addition to the above criteria, adverse events meeting either of the below criteria, although not serious per ICH definition, are reportable to the Sponsor in the same timeframe as SAEs to meet certain local requirements. Therefore, these events are considered serious by the Sponsor for collection purposes.

- Is a new cancer (that is not a condition of the study);
- Is associated with an overdose.

Refer to [Table 10](#) for additional details regarding each of the above criteria.

For the time period beginning when the consent form is signed until treatment allocation/randomization, any serious adverse event, or follow up to a serious adverse event, including death due to any cause other than progression of the cancer under study (reference Section 7.2.3.3 for additional details), that occurs to any subject must be reported within 24 hours to the Sponsor if it causes the subject to be excluded from the trial, or is the result of a protocol-specified intervention, including but not limited to washout or discontinuation of usual therapy, diet, placebo treatment or a procedure.

For the time period beginning at treatment allocation/randomization through 30 days following cessation of treatment, any serious adverse event, or follow up to a serious adverse event, including death due to any cause other than progression of the cancer under study (reference Section 7.2.3.3 for additional details), whether or not related to the Sponsor's product, must be reported within 24 hours to the Sponsor either by electronic media or paper. Electronic reporting procedures can be found in the EDC data entry guidelines. Paper reporting procedures can be found in the Investigator Trial File Binder (or equivalent).

Additionally, any serious adverse event, considered by an investigator who is a qualified physician to be related to the Sponsor's product that is brought to the attention of the investigator at any time following consent through the end of the specified safety follow-up

period specified in the paragraph above, or at any time outside of the time period specified in the previous paragraph also must be reported immediately to the Sponsor.

All subjects with serious adverse events must be followed up for outcome.

#### 7.2.3.2 Events of Clinical Interest

Selected non-serious and serious adverse events are also known as Events of Clinical Interest (ECI) and must be reported to the Sponsor.

For the time period beginning when the consent form is signed until treatment allocation/randomization, any ECI, or follow up to an ECI, that occurs to any subject must be reported within 24 hours to the Sponsor if it causes the subject to be excluded from the trial, or is the result of a protocol-specified intervention, including but not limited to washout or discontinuation of usual therapy, diet, placebo treatment or a procedure.

For the time period beginning at treatment allocation/randomization through 30 days following cessation of treatment, any ECI, or follow up to an ECI, whether or not related to the Sponsor's product, must be reported within 24 hours to the Sponsor, either by electronic media or paper. Electronic reporting procedures can be found in the EDC data entry guidelines. Paper reporting procedures can be found in the Investigator Trial File Binder (or equivalent).

Events of clinical interest for this trial include:

- an overdose of Sponsor's product, as defined in Section 7.2.1 - Definition of an Overdose for This Protocol and Reporting of Overdose to the Sponsor, that is not associated with clinical symptoms or abnormal laboratory results.
- an elevated AST or ALT lab value that is greater than or equal to 3X the upper limit of normal and an elevated total bilirubin lab value that is greater than or equal to 2X the upper limit of normal and, at the same time, an alkaline phosphatase lab value that is less than 2X the upper limit of normal, as determined by way of protocol-specified laboratory testing or unscheduled laboratory testing.\*

\*Note: These criteria are based upon available regulatory guidance documents. The purpose of the criteria is to specify a threshold of abnormal hepatic tests that may require an additional evaluation for an underlying etiology. The trial site guidance for assessment and follow up of these criteria can be found in the Investigator Trial File Binder (or equivalent).

1. an elevated total bilirubin lab value that is greater than or equal to 2X the upper limit of normal.
2. an elevated AST or ALT lab value that is greater than or equal to 5X the upper limit of normal.

\*Note: For further guidance on the monitoring, treatment and follow-up of any ECI related to potential drug-induced liver injury (DILI), please see Section 12.8.

3. For the purpose of this dose-finding study, any suspected DLT occurring during dose escalation will be considered as medically important and reported as an ECI. If the event also meets the criteria for seriousness, follow the reporting guidelines for Serious Adverse Events (SAEs) outlined in Section 7.2.3.1

